7.3.1.1. Additional Analyses of WHO FC

The rodatristat ethyl treatment groups will also be pooled and compared to placebo.

The same analyses specified above for Week 24 will be performed at Week 4 and 12.

In addition, treatment groups will be compared on response based on the following distributions of subjects at each visit using a stratified Cochran-Mantel-Haenszel (CMH) test (stratified by the randomization stratification factors) and a Fisher's exact test:

- WHO FC I or II vs WHO FC III or IV
- Any improvement in WHO FC vs no improvement
- Any worsening in WHO FC vs no worsening

7.3.2. Change from Baseline to Week 24 in 6MWD

The secondary efficacy analysis will test the following hypotheses:

- H_0 : The distribution of change from baseline at Week 24 in 6MWT distance (meters) is equal between placebo and rodatristat ethyl.
- H_1 : The distribution of change from baseline at Week 24 in 6MWT distance (meters) is different between placebo and rodatristat ethyl.

The change from baseline at Week 24 in 6MWT distance (meters) will be analyzed using the aligned rank stratified Wilcoxon test [Hodges, J. L., Jr. and Lehmann, E. L. 1962] [Mehrotra, D. V., et al 2010] with the randomization stratification factors as strata. In this test, the endpoint values are first aligned across the randomization strata using the stratum-level Hodges-Lehmann location shift estimates, and the aligned values are then analyzed using a Wilcoxon rank sum test. The output from this analysis will be used to provide a 2-sided p-value and corresponding Hodges-Lehmann location-shift estimate of the overall treatment difference with 95% confidence interval (CI). SAS implementation code for the aligned rank stratified Wilcoxon test is below

```
PROC NPAR1WAY DATA=data WILCOXON ALIGN=STRATA(HL) HL  
CORRECT=NO;  
CLASS trtp;  
VAR chg;  
STRATA strata;  
ODS OUTPUT HodgesLehmann=hlstats_a;  
RUN;
```

7.3.2.1. Additional Analyses of 6MWD

The rodatristat ethyl treatment groups will also be pooled and compared to placebo.

Additional analyses of the percent change from baseline in 6MWD will be analyzed the same manner. Analyses will be repeated for the Treatment Completer population.

Summaries will be provided for the subgroups as specified in [Section 7.1.7](#). A forest plot of the Hodges-Lehman estimate of the median treatment differences and 95% CIs will be presented for Placebo versus Rodatristat ethyl 300 mg BID and Placebo versus Rodatristat ethyl 600 mg BID for the ITT and Treatment Completer populations.

In addition to the secondary endpoint, 6MWT distance, change from baseline, and percent change from baseline to all visits will be analyzed in the same manner described above.

The 6MWT change from baseline will also be categorized as follows:

- ≥ 30 -meter decline or $\geq 10\%$ decline (Worsening)
- < 30 -meter decline or $< 10\%$ decline to < 30 -meter improvement or 10% improvement (No Change)
- ≥ 30 -meter improvement or $\geq 10\%$ improvement (Improvement).

The categorical change from baseline will be summarized by visit for each scheduled post-baseline visit. For each post-baseline visit ordinal logistic regression will be performed with 6MWT categorical change from baseline (Worsening, No Change, Improvement) as the dependent variable and factors for treatment group and randomization strata. Estimates of the proportional odds ratio comparing placebo and rodatristat ethyl and the 95% CI of the odds ratio will be presented. An odds ratio greater than 1 favors the rodatristat ethyl treatment group.

7.3.3. Change from Baseline to Week 24 in NT-proBNP

The secondary efficacy analysis will test the following hypotheses:

- H_0 : The mean change from baseline at Week 24 in NT-proBNP is equal between placebo and rodatristat ethyl.
- H_1 : The mean change from baseline at Week 24 in NT-proBNP is different between placebo and rodatristat ethyl.

Rodatristat ethyl and placebo will be compared on change from baseline using a REML based MMRM model including fixed effects for randomization strata, treatment group, categorical time point, and the treatment group \times time point interaction, and with the baseline value included as a covariate. In cases of missing data occurring at Week 24, missing data handling rules are specified in [Section 7.1.2](#).

The unstructured covariance model will be used. If the computational algorithm fails to converge, the following structures will be executed: heterogeneous Toeplitz, Toeplitz, heterogeneous First-Order Autoregressive [AR (1)], AR(1), heterogeneous compound symmetry (HCS), and compound symmetry (CS). The covariance structure converging to the best fit, as determined by Akaike's information criterion (AIC), will be used. The Kenward and Roger method will be used to calculate the denominator degrees of freedom for the test of fixed effects. All visits will be included in the model, with the primary comparison at the Week 24 visit.

Estimates of least-square (LS) means, standard errors (StdErr), and 95% CIs will be presented by treatment group. In addition, the LS mean difference comparisons between rodatristat ethyl and placebo, the StdErr of the difference, and 95% CI of the difference will be presented.

Descriptive statistics for NT-proBNP scores, change from baseline, and percent change from baseline will be presented by visit for each treatment group.

Assumptions for the REML based MMRM model will be checked, and if not satisfied, parametric analyses will be corroborated with appropriate nonparametric analyses, such as the Wilcoxon rank sum test stratified by randomization strata. The Hodges-Lehmann estimation of location shift and confidence interval will be produced. If the model residuals are not normally distributed, ANCOVA analysis based on ranked data will be performed.

7.3.3.1. Additional Analyses of NT-proBNP

The rodatristat ethyl treatment groups will also be pooled and compared to placebo.

In addition to the secondary endpoint, NT-proBNP, change from baseline, and percent change from baseline to all visits will be analyzed in the same manner described above.

Sensitivity analyses will be performed based on observed cases using the ITT population. Analyses will be repeated using the Treatment Completer population.

Summaries will be provided for the subgroups as specified in [Section 7.1.7](#) for the ITT Population. A forest plot of the LS differences and 95% CIs will be presented for Placebo versus Rodatristat ethyl 300 mg BID and Placebo versus Rodatristat ethyl 600 mg BID for the ITT and Treatment Completer populations.

An additional sensitivity analysis will evaluate the rate of decrease (ie, slope) of NT-proBNP using a general linear mixed effects model to compare treatment groups. The model will fit a random intercept and slope for each subject and will include fixed effects for treatment group, time, randomization strata, and treatment group \times time interaction. Time will be expressed in weeks as a continuous variable and will include all scheduled time points including baseline. An unstructured covariance structure will be used to model the within-subject errors. If the computational algorithm fails to converge, the following structures will be executed: heterogeneous Toeplitz, Toeplitz, heterogeneous First-Order Autoregressive [AR (1)], AR(1), heterogeneous compound symmetry (HCS), and compound symmetry (CS). The covariance

structure converging to the best fit, as determined by Akaike's information criterion (AIC), will be used. The Kenward and Roger method will be used to calculate the denominator degrees of freedom for the test of fixed effects. The null hypothesis of no difference in slopes between the treatment groups will be determined by testing the significance of the treatment group by time interaction term.

Estimates of the slope will be presented by treatment group along with corresponding 95% CIs. The estimate of the difference between slopes (Rodatristat ethyl -Placebo) and the 95% CI of the difference between slopes will also be presented. Appropriate contrasts for pairwise differences in coefficients at time points of interest between rodatristat ethyl and placebo with corresponding 95% CIs will be estimated from the model and tested for significance.

7.4. Additional/Exploratory Efficacy Analyses

7.4.1. Change from Baseline in Cardiac Index, mPAP, mRAP, SvO2 at rest, and PAC

Cardiopulmonary hemodynamics are being assessed by right heart catheterization (RHC). All required RHC parameters are being collected using the same methods at Screening/Randomization and Week 24.

[Table 10](#) lists the RHC parameters collected on the CRF, which will be manually adjudicated by blinded medical monitors.

Table 10: Collected RHC Parameters

SDTM Test Code (FTTESTCD)	SDTM Test Name (FTTEST)
DPAP	Diastolic Pulmonary Artery Pressure
SPAP	Systolic Pulmonary Artery Pressure
MRAP	Central Venous/Mean Right Atrial Pressure
PCWP	Pulmonary Capillary Wedge Pressure
LVEDP	Left Ventricular-end Diastolic Pressure
MEAN THERMCO	Thermodilution CO (Mean)
FICKCO	Fick CO
VO2MEAS	Measured VO2
CARDFIO2	FiO2 at measurement
ASSUMVO2	Assumed VO2
CARDART	Arterial Oxygen Saturation SaO2

SDTM Test Code (FTTESTCD)	SDTM Test Name (FTTEST)
CARDHEMO	Hemoglobin Concentration
SVO2	Mixed Venous Oxygen Saturation

Table 11 lists the RHC parameters derived in the EDC based on investigator assessed parameters above and all to be derived based on adjudicated values where applicable.

Table 11: Derived RHC Parameters

SDTM Test Code (FTTESTCD)	SDTM Test (FTTEST)	Derivation Formula
CI	Cardiac Index	$CI = CO \div BSA$ *CO=THERMCO, if THERMCO not used then $CO = FICKCO$
FICKCO	Fick CO (will not be summarized due to small sample sizes)	$FICKCO = VO_2 (VO_2MEAS \text{ or } ASSUMVO_2^+) / [(CARDART - SVO2) \times CARDHEMO \times 0.134]$ ⁺ If VO ₂ not measured Bergstra Equation used to determine assumed VO ₂ (ASSUMVO ₂). *FICKCO is measured when THERMCO was not available
MPAP	Mean Pulmonary Artery Pressure	$mPAP = (2 \times dPAP + sPAP)/3$
PAC	Pulmonary Artery Compliance	$PAC = SV / (sPAP - dPAP)$
PVR	Pulmonary Vascular Resistance	$PVR = [(MPAP - PCWP) \div CO] \times 80$ or if PCWP missing then $PVR = [(MPAP - LVEDP) \div CO] \times 80$ *CO=THERMCO, if THERMCO not used then $CO = FICKCO$
PVRI	Pulmonary Vascular Resistance Index	$PVRI = ((mPAP - PCWP)/CI) \times 80$ or If LVEDP was provided instead of PCWP use LVEDP in the formula instead of PCWP. $PVRI = ((mPAP - LVEDP)/CI) \times 80$

SDTM Test Code (FTTESTCD)	SDTM Test (FTTEST)	Derivation Formula
SV	Stroke Volume	$SV = CO \div HR \times 1000$ *CO=THERMCO, if THERMCO not used, then CO=FICKCO
SVR	Systemic Vascular Resistance	$SVR = [(MAP - MRAP) \div CO] \times 80$ *CO=THERMCO, if THERMCO not used, then CO=FICKCO
MAP	Mean Arterial Pressure	$MAP = (2 \times dBP + sBP) / 3$
SVRI	Systemic Vascular Resistance Index	$SVRI = 80 \times (MAP - MRAP) / CI$

Thermodilution and Fick Cardiac Output will be combined for summary purposes, where Thermodilution will be used primarily and Fick if Thermodilution is not available. PVR and LVEDP will be combined for summary purposes, where PVR will be used primarily and LVEDP if PVR is not available.

Primary analyses of hemodynamic parameters will be based on adjudicated data, where applicable, using the ITT and Treatment Completer populations, and sensitivity analyses will be based on investigator assessment as collected on the CRF. The change from baseline will be analyzed using the same ANCOVA model as specified in [Section 7.2](#).

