5. STUDY POPULATION

5.1. Inclusion Criteria

Patients are eligible to be included in the study only if all the following criteria are met:

- 1. Male and female patients must be at least 18 years of age at the time of signing the informed consent.
 - a. Male patients and female partners of childbearing potential must agree to use contraception as detailed in a Section 5.4.1 to the protocol starting at Screening, during the treatment period, and for at least 100 days after the last dose of IP. Male patients must refrain from donating sperm during this period.
 - b. Female patients of childbearing potential must agree to use contraception as detailed in Section 5.4.1 starting at Screening, during the treatment period, and for at least 4 weeks after the last dose of IP.
- 2. Body mass index (BMI) $\geq 18 \text{ kg/m}^2 \text{ and } \leq 40 \text{ kg/m}^2$
- 3. Patients with symptomatic PAH belonging to one of the following 2018 Clinical Group 1 sub-types:
 - a. Idiopathic PAH
 - b. Heritable PAH
 - c. Drug- or toxin-induced
 - d. PAH associated with:
 - 1. Connective tissue disease
 - 2. Congenital systemic to pulmonary shunt (atrial septal defect, ventricular septal defect, patent ductus arteriosus) repaired at least one year prior to Screening
 - 3. Human immunodeficiency virus (HIV) infection if diagnosed with HIV, must have stable disease status defined as follows:
 - a. stable treatment with HIV medications for at least 8 weeks prior to Screening
 - b. no active opportunistic infection during the Screening Period
 - c. no hospitalizations due to HIV for at least 4 weeks prior to Screening
- 4. WHO FC II or III
- 5. Confirmed diagnosis of PAH and meet all the following hemodynamic criteria by means of a screening RHC completed prior to randomization:
 - a. mPAP of >20 mmHg
 - b. $PVR \ge 350 \text{ dyne-sec/cm}^5$
 - c. Pulmonary capillary wedge pressure (PCWP) or left ventricular end diastolic pressure (LVEDP) of ≤ 12 mmHg if PVR ≥ 350 and < 500 dyne•sec/cm⁵, or PCWP/LVEDP ≤ 15 mmHg if PVR ≥ 500 dyne•sec/cm⁵
- 6. 6MWD of 100 to 550 meters at Screening

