3. SAMPLE SIZE JUSTIFICATION

The sample size for this study was not based on a formal hypothesis testing. It is expected that 30 evaluable subjects per arm will provide sufficient data to assess safety and efficacy. Power calculations were conducted to examine the probability of detecting a difference among treatment groups for the percentage change of PVR from baseline.

A sample size of 90 subjects with 30 subjects to be randomized into 1 of the 3 treatment arms in a 1:1:1 randomization is planned. A sample size of 30 subjects per arm will provide at least 80% power at a significance level of 0.05 (2-sided hypothesis) to detect a treatment difference of 0.75 times of standard deviation (SD) in the percentage change from baseline of PVR from baseline between an active arm and the placebo arm. If the SD for PVR percent change is 24%, the study has 80% power to detect a difference of 18% between an active arm and the placebo arm.

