7.1.2.1. Missing at Random (MAR): Multiple Imputation

For the primary analysis of PVR, 6MWT, and NT-proBNP efficacy endpoints, subjects who miss an assessment for reasons other than death or other tolerability reasons, will be imputed using multiple imputation (MI) methodology based on the treatment group for time points at which no value is observed. An intercurrent event meeting will be held prior to database lock and unblinding with the medical monitor(s) and statistician(s) to review the missing efficacy assessments for each subject and determine if the missing data is MAR or missing not at random, (MNAR), i.e. informative missing.

MI will be performed under the assumption of MAR. Intermittent missing value(s) will also be replaced using MI. MI will impute 10 integer values using Markov Chain Monte Carlo (MCMC) methods assuming nonmonotone missing, a seed of 100201, 500 burn-in iterations, 100 iterations between imputations, and a non-informative prior. The imputation models based on treatment group will include randomization stratification factors, baseline WHO FC, baseline 6MWD, and baseline value of the endpoint and all previous values of the endpoint at each time point. Other baseline characteristics that may be explored will be documented in the CSR. It is anticipated that the imputation model will converge but should it not do so terms will be removed from the model to achieve convergence. The effects of any such model adjustment will be investigated.

Change from baseline to each post-baseline visit will be calculated based on observed and imputed data. Results from the analysis of each of the 10 imputed datasets will be combined using PROC MIANALYZE (Rubin's imputation rules, [Rubin 1987](#)).

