7.2. Primary Efficacy Analysis

The primary efficacy analysis will test the following hypothesis:

- H_0 : The mean change from baseline in PVR at Week 24 is equal between placebo and rodatristat ethyl.
- H_1 : The mean change from baseline in PVR at Week 24 is different between placebo and rodatristat ethyl.

In cases of missing data occurring at Week 24, missing data handling rules are specified in [Section 7.1.2](#).

Percent change from baseline in PVR at Week 24 will be analyzed using an analysis of covariance (ANCOVA) model with terms of treatment, randomization strata and baseline PVR. Estimates of least-square (LS) means, standard errors (StdErr), and 95% CIs will be presented by treatment group. In addition, the LS mean difference comparisons between each active dose and placebo, the StdErr of the difference, and 95% CI of the difference will be presented.

In order to control the Type 1 error rate, the comparisons between each active arm and the placebo arm will be tested using the Hochberg approach, where the two p-values (600 mg vs placebo and 300 mg vs placebo) will be ordered largest to smallest as $p(1) > p(2)$.

1. If $p(1) < 0.05$ then reject both null hypotheses.
2. If $p(1) > 0.05$, but $p(2) < 0.025$, then reject the null hypothesis associated with $p(2)$.

Assumptions for the ANCOVA will be checked, and if not satisfied, parametric analyses will be corroborated with appropriate nonparametric analyses, such as the Wilcoxon rank sum test stratified by randomization strata. The Hodges-Lehmann estimation of location shift and confidence interval will be produced. If the model residuals are not normally distributed, ANCOVA analysis based on ranked data will be performed.

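### SAP 7.4.1 lets LVEDP stand in for a missing PVR in summaries, contradicting Table 11, where LVEDP stands in for a missing PCWP

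*SAP*

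**What the plan says.** SAP Section 7.4.1 sets out the right heart catheterization variables. Table 11 derives PVR as (mPAP − PCWP) ÷ CO × 80 and then adds an alternative, "or if PCWP missing then", in which LVEDP takes the place of PCWP. The PVRI row has the same fallback: "If LVEDP was provided instead of PCWP use LVEDP in the formula instead of PCWP".

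Two sentences of text follow the table. The first pools thermodilution and Fick cardiac output, using Fick where thermodilution is unavailable. The second reads: "PVR and LVEDP will be combined for summary purposes, where PVR will be used primarily and LVEDP if PVR is not available".

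The primary endpoint is handled elsewhere. Section 7.2 states: "Percent change from baseline in PVR at Week 24 will be analyzed using an analysis of covariance (ANCOVA) model". On gaps in the data it says: "In cases of missing data occurring at Week 24, missing data handling rules are specified in" Section 7.1.2. There, Section 7.1.2.1 begins "For the primary analysis of PVR, 6MWT, and NT-proBNP efficacy endpoints, subjects who miss an assessment for reasons other than death" and prescribes multiple imputation. Section 7.1.2.2 assigns the worst value in the planned treatment group when the reason is death, tolerability or a specified change in prostanoid dose. Neither mentions LVEDP.

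**The concern.** The sentence replaces a resistance with a pressure. The two quantities have different units, and their values here differ by a factor of roughly 25 to 125. Protocol Section 5.1 shows the scale: it requires a PVR of at least 350 dyne•sec/cm⁵ and sets wedge or LVEDP limits of 12 or 15 mmHg, for example "PCWP/LVEDP ≤ 15 mmHg if PVR ≥ 500 dyne•sec/cm⁵".

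Two things follow if a programmer applies the sentence as written:

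- A Week 24 PVR that could not be derived would be filled with a number in the teens or below. It would appear as a fall of well over 90%, whatever the patient's true response.
- PCWP and LVEDP, which are the natural pair, would not be combined for summaries. A patient with LVEDP only would drop out of the baseline PCWP summary planned in SAP Section 6.2.

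The phrase about summary purposes does not settle how far the rule reaches. The preceding sentence uses the same phrase for cardiac output, and Table 11 applies that cardiac output fallback inside the derivations themselves. Table 11 is also the only place where the SAP derives PVR.

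**Working it through.** **Inputs.** From the SAP: 30 per arm, difference 18 points, SD 24 points, two-sided 0.05 (Section 3); percent change = (later − baseline) ÷ baseline × 100 (Section 4.5); the formulas in Table 11. From the protocol: entry limits in Section 5.1. Assumed, because the documents do not give them: individual LVEDP and baseline PVR values, mPAP, CO, and the number of affected patients.

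**1. The plan's own figure.** Section 3 says: "A sample size of 30 subjects per arm will provide at least 80% power at a significance level of 0.05 (2-sided hypothesis") for a difference of 0.75 SD.
- Standard error = 24 × √(2/30) = 6.20, and 18 ÷ 6.20 = 2.90.
- Normal approximation: Φ(2.90 − 1.96) = 82.8%.
- Two-sample t-test: 81.5%.

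The stated power is reproduced. The point does not depend on it.

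**2. The two rules side by side.**

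| Place in SAP 7.4.1 | What is missing | What LVEDP replaces | Units agree? |
|---|---|---|---|
| Table 11, PVR row | PCWP | PCWP, inside the formula | yes, both mmHg |
| Table 11, PVRI row | PCWP | PCWP, inside the formula | yes, both mmHg |
| Sentence after Table 11 | PVR | PVR itself | no, mmHg for dyne•sec/cm⁵ |

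Table 11 gives sensible results. With assumed mPAP 45 mmHg and CO 5 L/min, a wedge pressure or LVEDP of 8, 12 or 15 mmHg gives (45 − 8) ÷ 5 × 80 = 592, 528 or 480 dyne•sec/cm⁵. The sentence would record 8, 12 or 15.

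**3. When the sentence can take effect.** Table 11 already uses LVEDP when PCWP is absent. PVR can therefore be missing with LVEDP present only if mPAP is missing (no systolic or no diastolic pulmonary pressure) or if both thermodilution and Fick output are missing. A patient with no Week 24 catheterization has no LVEDP from it either.

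**4. Where a substituted value would land.**
- PVR summaries: directly.
- Subgroup results (Section 7.1.7) and observed-case analyses (Section 7.1.2.4): possibly. These use no imputation, so a substituted value could pass as an observed PVR.
- Primary ANCOVA: only if the substitution is made when the analysis dataset is built. The record would then no longer look missing, and Section 7.1.2 would not be triggered.

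**5. Size for one patient (hypothetical).** Percent change at Week 24:
- LVEDP 12, baseline PVR 350: (12 − 350) ÷ 350 = −96.6%
- LVEDP 15, baseline PVR 500: −97.0%
- LVEDP 12, baseline PVR 700: −98.3%
- LVEDP 8, baseline PVR 1000: −99.2%

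No LVEDP limit applies at Week 24. An assumed 30 mmHg against a baseline of 350 still gives −91.4%.

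**6. Size for an arm of 30 (hypothetical).** With one value of −98%:
- True arm mean 0: (29 × 0 − 98) ÷ 30 = −3.27, a shift of −3.3 points. The SD rises from 24 to 29.6.
- True arm mean −18: (29 × −18 − 98) ÷ 30 = −20.67, a shift of −2.7 points. The SD rises from 24 to 27.7.

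The shift is always toward apparent benefit in that patient's arm. If such values did reach the comparison, the unadjusted normal-approximation power would go from 82.8% to about 56% (one in placebo only), 65% (one in each arm) or 87% (one in the active arm only).

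**The case against.** The strongest reply is that this is an editorial slip with little practical reach.

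- The sentence is limited to summaries and sits in the section on additional hemodynamics. The primary analysis has its own section and its own missing-data rule.
- The correct derivation stands immediately above. The neighbouring sentence pairs two measures of the same quantity, so PCWP is plainly what was meant.
- The set of affected patients is close to empty, for the reason in step 3.
- Catheterization data are adjudicated by blinded medical monitors, and odd values are to be resolved before database lock (Sections 7.1.3.2 and 7.1.3.3). A PVR of 10 or 15 against an entry minimum of 350 would stand out.

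Most of this stands. It limits frequency and reach, but it does not make the sentence correct. The sentence is an operative rule, it conflicts with the table above it, and the gap in the PCWP summary needs no rare missing-data pattern.

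A reader might infer more: that the primary endpoint will be corrupted, or that a missing Week 24 PVR will skip the planned imputation. The documents do not support that. Section 7.2 sends missing Week 24 PVR to Section 7.1.2, and nothing there admits LVEDP. A reader might also pair the 15 mmHg limit with a PVR of 350 to illustrate the size. That is not an eligible baseline pair, since Section 5.1 sets 12 mmHg for PVR from 350 to below 500, and no entry limit applies at Week 24.

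**Conclusion.** The sentence is wrong as written and contradicts Table 11. Its direct effects are on PVR summaries, possibly on the observed-case and subgroup PVR analyses, and on the PCWP summary, where LVEDP-only patients are left out. Few patients are likely to be affected through PVR; the documents give no count.

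Corruption of the primary result is a risk only if the substitution is built into the analysis dataset. The shift of 2.7 to 3.3 points, set against the 18 points in Section 3, illustrates one such patient in an arm of 30 with a value of −98% and a true arm mean of −18 or 0. It is not an estimate of what will happen. Sample size and stated power are unaffected.

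**What to change.** In the sentence after Table 11, write PCWP in all three places where PVR now stands, so that PCWP and LVEDP are pooled for summaries, with PCWP preferred and LVEDP used where PCWP is absent. Add one line saying that a PVR that cannot be derived from Table 11 stays missing and is handled only under Section 7.1.2. Carry both into the dataset specification, and check that no derived PVR equals the recorded LVEDP.

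The cost is one corrected term, one added line and one programming check. No analysis, sample size or clinical rule changes.
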